11.6. Programming Visit (45 ± 7 days post-Activation Visit)

At the Programming Visit, subjects' device will be programmed to receive optimal settings. Subjects will be asked about any adverse events since their last study visit (if any). Information related to programming will be collected.

End of Visit Information:

- Subjects should be reminded not to make any changes to their opioid medications (type/dose/route);
- Instructions related to charging and use of device should be provided per standard of care;
- Subjects will receive a 7-day diary to be completed prior to the 3-Month Visit. The diary may be completed in a 15-day window prior to the Visit.

11.7. 3-Month Visit (90 ± 14 days post-Activation Visit)

At the 3-Month Visit, subjects' will return to the clinic for programming and evaluation. Subjects will be asked about any adverse events since their last study visit (if any). Subjects will return their 7-day diary to the site staff.

The following assessments will be completed at 3-Month Visit prior to device programming.

- Pain Intensity: Numerical Rating Scale (NRS) as evaluated by study personnel interview
- Percent Pain Relief (PPR)
- Patient Global Impression of Change (PGI-C)
- Oswestry Disability Index version 2.1a (ODI v2.1a)
- Resource Utilization Inventory (RUI)
- Short Form Health Survey 36 items (SF-36 v2)
- 7-day Subject Diary

Per standard of care, subjects' device may be programmed as needed after completion of assessments. Information related to programming will be collected. Subjects' opioid medications may be adjusted as needed and change during the rest of the course of the study. Changes to opioid medications should be documented.

End of Visit Information:

- Instructions related to charging and use of device should be provided per standard of care.

11.8. 6-Month Visit (180 ± 30 days post-Activation Visit)

At the 6-Month Visit, subjects' will return to the clinic for programming and evaluation. Subjects will be asked about any adverse events since their last study visit (if any).

The following assessments will be completed at 12-Month Visit prior to device programming.

- Pain Intensity: Numerical Rating Scale (NRS) as evaluated by study personnel interview
- Percent Pain Relief (PPR)
- Patient Global Impression of Change (PGI-C)
- Oswestry Disability Index version 2.1a (ODI v2.1a)
- Resource Utilization Inventory (RUI)
- Short Form Health Survey 36 items (SF-36 v2)

Per standard of care, subjects' device may be programmed as needed after completion of assessments. Information related to programming will be collected. Subjects' opioid medications may be adjusted as needed and change during the rest of the course of the study. Changes to opioid medications should be documented.

End of Visit Information:

- Instructions related to charging and use of device should be provided per standard of care;
- Subjects will receive a 7-day diary to be completed prior to the 12-Month Visit. The diary may be completed in a 15-day window prior to the Visit.

11.9. 12-Month Visit (365 ± 30 days post-Activation Visit) - End of Study

At the 12-Month Visit, subjects' will return to the clinic for programming and evaluation. Subjects will be asked about any adverse events since their last study visit (if any). This Visit will be End of Study Visit and subjects will be followed per End of Study Action Plan as described in Section 10.5. Subjects will return their 7-day diary to the site staff.

The following assessments will be completed at 12-Month Visit prior to device programming.

- Pain Intensity: Numerical Rating Scale (NRS) as evaluated by study personnel interview
- Percent Pain Relief (PPR)
- Patient Global Impression of Change (PGI-C)

- Short Form Health Survey 36 items (SF-36 v2)
- Resource Utilization Inventory (RUI)
- Oswestry Disability Index version 2.1a (ODI v2.1a)
- 7-day Subject Diary

Per standard of care, subjects' device may be programmed as needed after completion of assessments. Information related to programming will be collected. Subjects' opioid medications may be adjusted as needed and change during the rest of the course of the study. Changes to opioid medications should be documented.

End of Visit Information:

- Instructions related to charging and use of device should be provided per standard of care.

11.10. *Unscheduled Study Visits*

Subjects may have as many unscheduled study visits as needed for programming (e.g., reprogramming, replacement, revision) or evaluation of adverse events.

11.11. *Revision or Replacement of Leads, Extensions and/or IPGs*

During the course of the study, it is possible that leads may be placed incorrectly, migrate, or malfunction and require repositioning or replacement. It is also possible that the extensions or splitters or IPG may be uncomfortable or malfunction and may require repositioning or replacement. The decision to reposition or replace any device component will be made by the investigator and only if the subject agrees. Subjects not agreeing to a recommended lead revision will be withdrawn from the study but will be included in the intent-to-treat and safety analyses. Subjects agreeing to revision will continue on study and will be followed according to the original study schedule. Effectiveness data from these subjects will be included in the intent to treat analysis. Any replacements or revisions performed during the course of the study must be documented. Acute opioid pain medications may be taken per standard of care.

11.12. *Study Completion*

All subjects permanently implanted with an IPG will be followed through completion of the End of Study visit (12-months post-Activation Visit). The End of Study Action Plan (see Section 10.5) defines the actions to be taken when the subject reaches the end of their study participation.

11.13. *Source Documents*

Where copies of the original source document as well as printouts of original electronic source documents are retained, these shall be signed and dated by a member of the

investigation center team with a statement that it is a true reproduction of the original source document.

Table 11-2: Source Documentation Requirements

Requirement	Disposition
Hospital records and/or clinical and office charts including the evidence of but not limited to inclusion/exclusion criteria, informed consent, procedures, laboratory results, medications, assessment of adverse events, health resource utilization information	Retained at investigational site
Imaging films/prints documenting lead(s) location	Retained at investigational site
Assessments and questionnaires	Retained at investigational site and/or electronic data collection platform / EDC
Clinician programmer printouts/electronic files for programming information	Retained at investigational site

12. Statistical Considerations

12.1. Primary Endpoint

The primary endpoint for this study is low back responder rate at 3 months post-activation,

[REDACTED]

[REDACTED]

[REDACTED]

[REDACTED]

12.1.1. Hypotheses

[REDACTED]

12.1.2. Sample Size

The required sample size for this study was calculated based on the following assumptions:

Term	Percentage
GMOs	85%
Organic	75%
Natural	70%
Artificial	65%
GMOs	60%
Organic	55%
Natural	50%
Artificial	45%
GMOs	35%
Organic	30%
Natural	25%
Artificial	20%

12.1.3. Statistical Methods

For the primary endpoint, statistical testing will be performed to determine if the low back pain responder rate with HR-SCS is superior to the OPC of this study.

The statistical test will be a Fisher's Exact test for a single proportion.

12.2. Secondary Endpoints

Term	Percentage
GDP	95
Inflation	95
Interest rates	85
Central bank	80
Monetary policy	75
Quantitative easing	70
Inflation targeting	65
Interest rate hike	60
Interest rate cut	55
Inflationary spiral	50

12.3. Exploratory Endpoints

A number of exploratory endpoints are included in this study to explore the effect of treatment on additional outcomes.

The exploratory endpoints are intended to generate hypotheses for future study. Consequently, no correction for multiple testing will be performed for the exploratory endpoints. All exploratory endpoints will be clearly identified as such in study reports.

12.4. Health Economic Endpoints

A number of health economic endpoints are included in this study to measure the economic value of the treatment.

12.5. Safety Parameters

Safety parameters include the Rate of occurrence of all device or procedure related adverse events (AEs), SAEs including serious adverse device events (SADEs), unanticipated serious adverse device effects (USADEs) through end of study.

For time-to-event variables, Kaplan-Meier plots will be provided. The Cox proportional hazards regression model will be used to assess the effects of risk factors on the time-to-event variables.

12.6. Analysis Sets

All primary and secondary endpoints will be analyzed on both intent-to-treat and a per-protocol basis.

12.6.1. Safety Analysis Set

In the safety analysis, all subjects who sign the IRB-approved written Informed Consent form will be included.

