11.2. Screening Period (Up to 60 days following Informed Consent)

All interested patients will undergo a screening period during which their eligibility into the study will be determined.

Written Informed Consent must be obtained for all subjects who are potential study candidates. A subject is considered enrolled only after the subject signs and dates the ICF:

- Subjects will be asked to sign the Informed Consent form before any study-specific tests or procedures are performed;
- The context of the study must be fully explained and the subjects must be given the opportunity to ask questions and have those questions answered to their satisfaction;
- Study personnel should explain that even if a subject agrees to participate in the study and signs an ICF, certain procedures might demonstrate that the patient is not eligible to continue participation;
- The Informed Consent form is study-specific and must be approved by the Ethics Committee (EC).

During the Screening period, eligibility criteria as described in Sections 9.2 and 9.3 will be evaluated. If a subject fails study eligibility, they will be withdrawn from the study.

Subjects will complete a 7-day daily diary (consecutive) to document their pain scores and return the diary to the site staff at the Baseline Visit. This diary may be completed in a 15-day window prior to the Baseline Visit.

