11.4. SCS Implant Procedure (s)

Subjects will have up to 45 days to receive their Precision SCS Implant after the Baseline visit. Subjects will undergo a screening trial and implant procedure based on the sites' standard of care.

- Information related to the procedure, devices, etc. will be documented.
- Only BSC percutaneous leads may be used. Surgical/Paddle leads may not be used.
- Intraoperative Testing may be performed per standard of care
- The IPG may be programmed but, following the completion of programming, the device will be OFF until the Device Activation Visit
- The use of acute opioid pain medication for procedural discomfort is allowed, per site's routine care.

End of Visit Information: Following the implant procedure, instructions related to follow up care will be provided per standard of care.

- Subjects are to contact the site in an event that any additional intervention is warranted, to report a suspected adverse event, etc.
- Subjects should be reminded not to make any changes to their opioid medications (type/dose/route)
- If device implantation is unsuccessful, subjects will be followed for 2 weeks post implantation in an attempt to assess for procedure related adverse events, if they occur. These subjects will be withdrawn from the study.

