20.1 Definitions and Classification

Adverse event definitions are provided in **Error! Reference source not found.**

Table 20-1: Safety Definitions

Term	Definition
Adverse Event (AE) Ref: ISO 14155-2011 Ref: MEDDEV 2.7/3 12/2010	Any untoward medical occurrence, unintended disease or injury, or any untoward clinical signs (including an abnormal laboratory finding) in subjects, users or other persons, whether or not related to the investigational medical device. NOTE 1: This includes events related to the investigational medical device or comparator. NOTE 2: This definition includes events related to the procedures involved (any procedure in the clinical investigation plan). NOTE 3: For users or other persons, this definition is restricted to events

Table 20-1: Safety Definitions

Term	Definition
	related to the investigational medical device.
Adverse Device Effect (ADE) Ref: ISO 14155-2011 Ref: MEDDEV 2.7/3 12/2010	Adverse event related to the use of an investigational medical device NOTE 1: This definition includes any adverse event resulting from insufficient or inadequate instructions for use, the deployment, the implantation, the installation, the operation, or any malfunction of the investigational medical device. NOTE 2: This definition includes any event resulting from use error or from intentional misuse of the investigational medical device.
Serious Adverse Event (SAE) Ref: ISO 14155-2011 Ref: MEDDEV 2.7/3 12/2010	Adverse event that: a) Led to death, b) Led to serious deterioration in the health of the subject, that either resulted in: a life-threatening illness or injury, or a permanent impairment of a body structure or a body function, or in-patient or prolonged hospitalization of existing hospitalization, or medical or surgical intervention to prevent life-threatening illness or injury or permanent impairment to a body structure or a body function c) Led to fetal distress, fetal death, or a congenital abnormality or birth defect. NOTE 1: Planned hospitalization for a pre-existing condition, or a procedure required by the clinical investigational plan, without serious deterioration in health, is not considered a serious adverse event.
Serious Adverse Device Effect (SADE) Ref: ISO 14155-2011 Ref: MEDDEV 2.7/3 12/2010	Adverse device effect that has resulted in any of the consequences characteristic of a serious adverse event.

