20.2 Relationship to Study Device(s)

The Investigator must assess the relationship of the AE to the study device or procedure. See criteria in **Error! Reference source not found.**

Table 20-2: Criteria for Assessing Relationship of Study Device or Procedure to Adverse Event

Classification	Description
Unrelated	The adverse event is determined to be due to a concurrent illness or effect of another device/drug and is not related to the investigational product.
Related	d) The adverse event is determined to be potentially related to the investigational product, and an alternative etiology is equally or less likely compared to the potential relationship to investigational product, or e) There is a strong relationship to investigational product, or recurs on re-challenge, and another etiology is unlikely, or There is no other reasonable medical explanation for the event.

The Investigator must assess the potential relationship of all adverse events to the **device and procedure**. All **device** related adverse events will be assessed according to their relationship to one of the following sub-categories:

- **Device Hardware-Related AEs:** AEs that can reasonably be attributed to the mere physical presence of the device or to deficiency of the device (i.e., an allergic response to device materials).
- **Stimulation-Related AEs:** AEs that can reasonably be attributed to the effects of stimulation. A relationship to stimulation may be determined by demonstrating a predictable response to the alternating between stimulation-on and stimulation-off settings. However, a relationship to stimulation may also be reported without demonstrating a predictable response to the alternating between the stimulation-on and stimulation-off settings if in the opinion of the Investigator the AE is potentially related to stimulation.
- **Procedure Related AEs:** AEs that can reasonably be attributed to a **study protocol required procedure**.

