20.3 Investigator Reporting Requirements

The communication requirements for reporting to BSC are as shown in **Error! Reference source not found.**3.

Table 20-3: Investigator Reporting Requirements

Unanticipated Serious Adverse Device Effect	Complete AE eCRF page with all available new and updated information	
• Within 1 business day of first becoming aware of the event.• Terminating at the end of the study
---	--	---

Table 20-3: Investigator Reporting Requirements

Serious Adverse Event including Serious Adverse Device Effects	Complete AE eCRF page with all available new and updated information	
 Within 2 business days of first becoming aware of the event or as per local/regional regulations. Reporting required through the end of the study
	Provide all relevant source documentation (unidentified) for reported event	
 When documentation is available
Adverse Event	Complete AE eCRF page, which contains such information as date of AE, treatment of AE resolution, assessment of seriousness and relationship to the device	
 In a timely manner (e.g. Recommend within 10 business days) after becoming aware of the information Reporting required for adverse events related to procedure, hardware and stimulation. Reporting is required through the end of the study.
Device Deficiencies (including but not limited to failures, malfunctions, and product nonconformities) Note: Any Investigational Device Deficiency that might have led to a serious adverse event if a) suitable action had not been taken or b) intervention had not been made or c) if circumstances had been less fortunate is considered a reportable event.	Complete Device Deficiency eCRF with all available new and updated information	
 Within 2 business day of first becoming aware of the event and as per local/regional regulations Reporting required through the end of the study

Note:

- AEs related to device/procedure, SAEs, SADEs, Device Deficiencies and USADEs will be collected from the time of informed consent through end of study. SAEs and Device Deficiencies may be reported via phone, fax or email if the electronic data capture (EDC) system is unavailable. The paper SAE Notification Form or Device Deficiency Notification Form should be used to report SAEs and/or device deficiencies during this time.

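### If the related-event rate is a proportion of subjects, the all-consented safety set dilutes it with subjects who left before any trial or implant; the visible text defines neither the rate nor an exposed denominator (minor)

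*Combined protocol and SAP*

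**What the plan says.** Section 12.6.1 sets the population: "In the safety analysis, all subjects who sign the IRB-approved written Informed Consent form will be included". It is the only subsection under Analysis Sets in the table of contents. Section 10.1 places enrolment at the signing of consent and brings every enrolled subject into the analyses.

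The measure is in 12.5, repeated from 7.5 and the synopsis: "Safety parameters include the Rate of occurrence of all device or procedure related adverse events (AEs", followed by the serious categories. No unit or time origin is visible. Section 12.5 adds "For time-to-event variables, Kaplan-Meier plots will be provided" and a Cox model, without naming the variables.

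On who is exposed, 11.2 says "If a subject fails study eligibility, they will be withdrawn from the study". Section 10.3 confirms that ineligible subjects are not implanted. The screening trial and implant come after Baseline (11.4). A failed implant is treated differently: "If device implantation is unsuccessful, subjects will be followed for 2 weeks post implantation", to look for procedure-related events.

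On what counts as an event, 20.3 states "AEs related to device/procedure, SAEs, SADEs, Device Deficiencies and USADEs will be collected from the time of informed consent through end of study". Procedure-related events are defined broadly. The adverse event definition in 20.1 notes "This definition includes events related to the procedures involved (any procedure in the clinical investigation plan", and 20.2 ties procedure-relatedness to a "study protocol required procedure".

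On numbers, the synopsis and 10.4 cap the study at 60 implanted subjects, and 10.3 leaves non-implanted subjects out of the cap. Sections 8.1 and 12.8 set the maximum of 60 on enrolment, which under 10.1 happens at consent.

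**The concern.** A subject withdrawn in screening has had no lead, no pulse generator and no stimulation, so cannot have an event related to hardware, stimulation, the screening trial or the implant. In a per-subject proportion on the 12.6.1 set, such a subject adds one to the denominator and can add nothing to the numerator. The reported rate then depends partly on how many consented subjects fail screening, which says nothing about the device. The direction is fixed: the rate can only look lower.

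The study has one arm and aims to characterise real-world outcomes, so a reader has no concurrent rate against which the dilution would cancel. The stake is limited to the reported safety profile, because no visible hypothesis or stopping rule uses this rate.

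**Working it through.** The documents give no safety rate, screen-failure rate or precision target, so there is no figure of the plan's own to reproduce. The check is an identity with illustrative inputs.

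**Inputs from the documents.** The cap is 60 implanted subjects, and non-implanted subjects fall outside it (synopsis, 10.3, 10.4). The safety set is all consented subjects (12.6.1). Screening lasts up to 60 days (11.2). Participation lasts about 12–15 months (8.1).

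**Assumed inputs.** 10% or 20% of consented subjects are never exposed, and 12 exposed subjects have a related event.

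**Per-subject proportion.** With x subjects with events, E exposed and C consented:

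x/C = (x/E) × (E/C)

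Take E = 60. Then C = 60/(1 − 0.10) = 66.7, rounded up to 67, or 60/(1 − 0.20) = 75. Intervals are exact (Clopper-Pearson) 95%.

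| Denominator | Rate | 95% CI | Factor E/C |
|---|---|---|---|
| 60 exposed | 12/60 = 20.0% | 10.8–32.3 | 1 |
| 67 consented | 12/67 = 17.9% | 9.6–29.2 | 60/67 = 0.896 |
| 75 consented | 12/75 = 16.0% | 8.6–26.3 | 60/75 = 0.80 |

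With 6 events, 10.0% becomes 9.0% or 8.0%. With 18 events, 30.0% becomes 26.9% or 24.0%.

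**Failed trials count as exposed.** The 0.80 factor assumes that all 15 non-implanted subjects left before any procedure. If 6 of them had a failed screening trial, E = 66. The exposed rate is 12/66 = 18.2% (9.8–29.6), against 12/75 = 16.0%. The factor is 66/75 = 0.88, a relative loss of 12%.

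**No events observed.** The one-sided 95% upper bound is 1 − 0.05^(1/n). It gives 4.9% at n = 60, 4.4% at n = 67 and 3.9% at n = 75. The bound tightens although no exposure has been added.

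**Person-time from consent.** A screen failure adds at most about 2 months. Sixty completers contribute 60 × 12 = 720 or 60 × 15 = 900 months.

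- 7 screen failures add 14 months: 720/734 = 0.981 or 900/914 = 0.985, a loss of 1.5–1.9%.
- 15 screen failures add 30 months: 720/750 = 0.960 or 900/930 = 0.968, a loss of 3.2–4.0%.

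A rate per device-month has no such dilution. Nor does a Kaplan-Meier curve in which these subjects are censored at withdrawal, before anyone could have a trial- or implant-related event.

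**The case against.** **The effect is conditional.** It needs a per-subject rate and some loss before exposure, and the documents give neither. The only methods named in 12.5 are Kaplan-Meier and Cox, which would largely avoid the problem. This stands. A reader might infer that the plan will understate related events by 10–20%. The documents do not support that, because both the rate type and the screening losses are unknown.

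**The definition may be in text that is not public.** The body of 12.9 (on eligibility, exclusions and missing data), 13.2.1 on adverse events, parts of 12.10.4 and 12.11, and a block after 10.1 cannot be read. Any of them could hold a rate definition or an exposed denominator. This also stands, so the point is limited to what is visible and does not say that the sponsor has no definition.

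**The consented set is coherent.** Events are collected from consent, and procedure-related events include those from protocol procedures before the trial or implant. A reader might infer that 12.6.1 is simply wrong. It is not: the set suits listings, any-cause serious events and those earlier procedure-related events. It fits device- and implant-related proportions poorly.

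**The data are mostly recoverable.** Reasons for non-implantation (10.3, 12.7) and procedure information (11.4) are recorded, and 10.2 already refers to a site's total of trialled subjects. This lowers the severity, though a denominator chosen at reporting is weaker than one stated beforehand.

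**Consented numbers.** From 8.1 and 12.8 with 10.1, a reader might infer that only 60 will consent and fewer will be exposed. The explicit rule in 10.3 and 10.4, and the synopsis, say otherwise. The wording in 8.1 and 12.8 is most naturally loose, so no size estimate here rests on that reading.

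**Conclusion.** The point holds as a minor one with a cheap remedy. Section 12.6.1 states a rule that admits unexposed subjects. On a per-subject reading, device- and implant-related rates are multiplied by exposed/consented. Under the assumed shares, an exposed rate of 20.0% would read 17.9% or 16.0%; with six failed trials counted as exposed, 18.2% would read 16.0%. The 4.0-point shift from 20.0% to 16.0% lies well inside the sampling interval, which spans 32.3 − 10.8 = 21.5 points, but it always runs in the same direction.

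The sizes rest on three assumptions: a per-subject proportion, 10% or 20% of consented subjects unexposed, and 12 subjects with events. The effect is zero if nobody leaves before exposure. It is a few percent in relative terms or less for person-time, and absent when such subjects are censored before the exposure period. The conclusion covers the visible text only.

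**What to change.** 1. In 12.5, state the rate type and, where time enters, the time origin.
2. In 12.6.1, keep the consented set for adverse event listings, any-cause serious events and events from protocol-required procedures before the trial or implant.
3. Add one exposed set: all subjects in whom a screening-trial or implant procedure was started, including failed trials and unsuccessful implants. Use it as the denominator for device-related and trial- or implant-procedure-related adverse events, SADEs and USADEs. One such set is enough for a study of about 60 implanted subjects.
4. Report the numbers consented, exposed and implanted beside each rate.
5. Align the limit of 60 in 8.1 and 12.8 with the cap on implanted subjects in the synopsis, 10.3 and 10.4.

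If the non-public text already settles items 1 and 3, a cross-reference from 12.5 and 12.6.1 is sufficient.

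The cost is mainly analysis wording. The sponsor should confirm that the case report form shows whether a trial procedure was started. The downside is a second safety denominator to explain and somewhat higher reported related-event rates: by a factor of 67/60 = 1.12 or 75/60 = 1.25 under the assumed shares, or 75/66 = 1.14 with six failed trials counted as exposed.
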